5.2.2. Secondary Endpoints

- PK for rhu-pGSN including, but not limited to maximum concentration (C_{max}), time to maximum concentration (T_{max}), terminal half-life ($T_{1/2}$), area under the curve from time zero to 8 hours (AUC_{0-8}), area under the curve from time zero to infinity (AUC_{inf}) (levels measured within 30 minutes predose, 5-10 minutes after the end of administration, and 2, 8, 12 and/or 16, and 24 hours (\pm 30 minutes) after each dose (Day 3 sampling in multiple-dose arms is optional)

- Incidence, causality, and severity of AEs and SAEs graded according to the NCI CTCAE version 4.03 (or equivalent); clinically significant laboratory and/or EKG abnormalities as required by SOC; death irrespective of cause; cause of death per investigator, including relationship to study drug; use of vasopressors, intubation, or transfer to the ICU or equivalent through Day 28 (secondary time point)

5.2.3. Exploratory Endpoints

- Baseline and sequential pGSN levels
- Clinical outcomes: 28-day survival; ICU days; days on ventilator or pressers; days on antibiotics; duration of hospitalization; Δ SOFA and CURB-65 scores
- Temporal profiles of inflammatory biomarkers
- Pathogen type (bacterial; viral; other; unknown) determined per customary work-up at each site

5.2.4. Immunogenicity Endpoints

- Presence of anti-rhu-pGSN antibodies at Day 28

6. INVESTIGATIONAL PLAN

6.1. Overall Study Design

Study BTI-201 is a Phase 1b/2a, double-blind, placebo-controlled, dose-escalation study to evaluate the safety, PK, and pharmacodynamics of rhu-pGSN added to SOC in subjects hospitalized for acute CAP. Each dosing cohort will include 8 subjects randomized 3:1 rhu-pGSN:placebo (6 rhu-pGSN subjects:2 placebo subjects).

Dose will be based on actual body weight. Dose escalation will involve 3 dose levels of rhu-pGSN (6, 12, and 24 mg/kg) in patients admitted for CAP. Dose escalation will only occur after post-therapy safety information on all subjects in the prior cohort has been reviewed at Day 7 for the single-dose [SD] and multiple-ascending dose [MAD] arms.

The MAD portion of the study will commence once single doses of 6 mg/kg of rhu-pGSN are shown to be acceptably safe. The first 2 doses must be administered in the hospital, but the third dose can be given in a monitored outpatient setting where appropriate.

Discharged subjects will return for follow-up 7 days after the initiation of therapy (Day 7) and on Day 28 for the End-of-Study (EOS) Visit.

To assess safety and tolerability, subjects will undergo physical examinations (PE; including vital sign measurements), AE assessments, concomitant medication assessments, safety laboratory testing and EKGs (completed locally), and other testing as per local custom. See [Table 5](#) and [Table 6](#) for schedules of all study events.

6.2. Study Enrollment Plan

After informed consent, subjects with a primary diagnosis of CAP to be admitted to the medical wards will be screened for eligibility as soon as possible. Medical history, including concomitant medications and current clinical status, will be recorded. Initial assessments include:

- Pregnancy test (urine/blood) for women of childbearing potential
- A CXR and/or computed tomography (CT) of the chest if not previously completed in preceding 36 hours
- If inclusion and exclusion criteria are satisfied ([Section 7.2](#) and [Section 7.3](#)), the subject will be enrolled and assigned to a baseline risk group CURB-65 ≤ 3 or >3 . Randomization will not be stratified by risk group. Screening labs can be used for baseline values and need not be repeated unless the caregivers deem necessary. The day of admission will be used as baseline (Day 1) for analysis purposes. Subjects will receive rhu-pGSN or placebo at the assigned dose within 36 hours of presentation.

6.3. Doses and Schedule of Administration

In the SD arm, subjects will receive one dose of rhu-pGSN or placebo on Day 1 as an IV push at 6 mg/kg.

In the MAD arms, subjects will receive once-daily doses approximately 24 hours apart of rhu-pGSN or placebo on Days 1 through 3 as an IV push at 6, 12, or 24 mg/kg. The first 2 doses

must be administered in the hospital, but the third dose can be given in a monitored outpatient setting where appropriate.

6.4. Data and Safety Monitoring Board

An DSMB will be established to monitor safety of subjects. The DSMB will be comprised of 3 members: a representative of the Contract Research Organization (CRO), a representative of the Sponsor, and an independent expert in CAP.

Safety through Day 7 of the study will be evaluated after the completion of each dosing arm to determine if it is safe to initiate the next cohort according to the safety criteria for stopping doses (Section 6.5).

Further details will be included in the DSMB charter.

6.5. Safety Criteria for Stopping Doses

Dosing of rhu-pGSN may be stopped during the study at the discretion of the DSMB. In general, doses should not be interrupted for Grade 1 AEs, but treatment to control symptoms should be provided, if applicable.

6.5.1. Management of rhu-pGSN Injection-Related Reactions

Injection-related reactions (IRRs) (Table 3) will be defined according to the NCI-CTCAE, version 4.03 or higher.

Table 3: Definition of Injection-Related Reactions

Adverse Event	Grade 1	Grade 2	Grade 3	Grade 4
IRR	Mild transient reaction; injection interruption not indicated; intervention not indicated	Therapy or injection interruption indicated but responds promptly to symptomatic treatment (e.g., antihistamines, NSAIDs, narcotics, IV fluids); prophylactic medications indicated for ≤24 hours	Prolonged (i.e., not rapidly responsive to symptomatic medication, brief interruption of injection, or both); recurrence of symptoms following initial improvement; hospitalization indicated for clinical sequelae	Life-threatening consequences; urgent intervention indicated

Abbreviations: IRR=injection-related reaction; IV=intravenous; NSAIDs=non-steroidal anti-inflammatory drugs.

Management of Grade 1 IRRs

If a subject presents with a Grade 1 IRR:

- The injection may be continued; however, the rate may be reduced to 50% at the discretion of the Investigator.
- If the symptoms resolve, the injection can be increased, as tolerated, to the baseline rate.
- The subject may receive appropriate further treatment for IRRs if clinically indicated per the site's standard practice for management of IRRs.

Management of Grade 2 IRRs

If a subject presents with a Grade 2 IRR:

- The injection should be stopped immediately.
- The subject should receive appropriate further treatment with an antihistamine and/or acetaminophen (paracetamol) if clinically indicated per the site's standard practice for management of IRRs. Further medications can be administered if necessary.
- Once the symptoms have been resolved or reduced to Grade 1, the injection can be continued at an injection rate of 50%.
- If a subject who developed a Grade 2 IRR receives further injections, then premedication following the site's standard practice for premedication for IRR should be given before all subsequent injections of rhu-pGSN given at a rate of 50% of the original rate.

Management of Grade 3 IRRs

If a subject presents with a Grade 3 IRR:

- The injection should be stopped immediately.
- The subject must receive appropriate treatment with an antihistamine and/or acetaminophen (paracetamol) and/or methylprednisolone (or equivalent) and, if necessary, further medications (i.e., epinephrine, bronchodilator).
- Only after the complete resolution to \leq Grade 1, and after having received appropriate prophylactic medication(s) as described above, the injection may be resumed at an injection rate of 25%. If, after 1 hour, the subject's symptoms do not return and vital signs are stable, the injection rate may be increased to a maximum of 50%.
- If, after the resumption of injection, symptoms return (irrespective of grade), the injection must be stopped immediately and the injection tubing should be disconnected from the subject.
- Subjects experiencing a Grade 3 IRR may only receive further injections of study drug, provided clinically appropriate precautions are undertaken and agreed upon by Investigator and Medical Monitor.

Management of Grade 4 IRRs

If a subject presents with a Grade 4 IRR:

- The injection should be stopped immediately and the injection tubing should be disconnected from the subject.
- The subject should receive appropriate treatment with an antihistamine and/or acetaminophen (paracetamol) and/or methylprednisolone (or equivalent) and, if necessary, further medications (i.e., epinephrine, bronchodilator).
- The subject must not receive further injections of rhu-pGSN if rhu-pGSN is judged by the Investigator to be the cause of the IRR.

6.6. Study Duration

Subjects in the SD arm of the study will be treated for 1 day. Subjects in the MAD arms of the study will be treated for 3 consecutive days.

Subject screening: within 24 hours of presentation to hospital; enrollment and initiation of study treatment within 36 hours of presentation.

Subjects are followed for safety and efficacy through Day 28 for a total duration of approximately 1 month.

6.7. Total Duration of Subject Participation

Subjects will be observed for 28-days post-first dose.

6.8. End of Study Definition

End of study (EOS) will be defined as the date the last subject completes the EOS Visit. The Sponsor will notify all applicable regulatory agencies in accordance with local requirements when the study has ended.

6.9. Criteria for Treatment Discontinuation

Subjects are free to discontinue their participation in the study at any time and without prejudice to further treatment. The Investigator must withdraw any subject from the study if that subject requests to be withdrawn, or if it is determined that continuing in the study would result in a significant safety risk to the subject.

The subject's participation in this study may be discontinued for the following reasons:

- Subject withdrew consent
- Unacceptable AE
- Subject is unwilling or unable to continue the study or is lost to follow up
- Subject is non-compliant with study procedures/study protocol
- Investigator decides that withdrawal from the study is in the best interest of the subject

- Any clinically significant change in subject's medical condition (at the discretion of the Investigator)
- Sponsor decision to end the study

If a subject withdraws from the study prematurely, assessments scheduled for the EOS Visit should be performed as soon as possible. If a subject refuses further assessment, the subject should be contacted for safety evaluations (AE/concomitant medications/potential pregnancy) approximately 28 days after study withdrawal.

If such withdrawal occurs, or if the subject refuses to participate in the EOS Visit, the Investigator must determine the primary reason for a subject's withdrawal from the study and record the information on the electronic case report form (eCRF). If the reason for withdrawal is an AE, monitoring should continue until the outcome is evident. The specific event or test result(s) must be recorded in the eCRF. At the discretion of the Sponsor, subjects may also be removed from the study (Section 6.6).

It should be clearly documented in the source data whether a subject withdrew his/her consent and will not enter the follow-up phase, or if a subject withdrew his/her consent for study drug treatment but will continue further participation in the study.

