10.1.2. Serious Adverse Event (SAE)

A serious adverse event (SAE) is an AE occurring during any study phase (i.e., baseline, treatment, or follow-up), and at any dose of the investigational product, comparator or placebo, that fulfils one or more of the following:

- Results in death
- It is immediately life-threatening
- It requires in-patient hospitalization or prolongation of existing hospitalization
- It results in persistent or significant disability or incapacity
- Results in a congenital abnormality or birth defect
- It is an important medical event that may jeopardize the subject or may require medical intervention to prevent one of the outcomes listed above.

All SAEs that occur after a subject has signed the consent form and has been randomized, including before or during treatment and within 28 days following the cessation of treatment, whether or not judged to be related to the study, must be recorded on forms provided by the Sponsor.

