10.7. Reporting Adverse Events

All AEs, serious and nonserious, will be fully documented on the appropriate eCRF. For each AE, the Investigator must provide its duration (start and end dates or ongoing), intensity, assessment of causality and whether specific action or therapy was required.

All AEs that occur from the signing of the informed consent form (ICF) until the first dose of study drug should be recorded on the AE eCRF page only if the event was related to a study procedure. All other AEs/findings prior to first dose of study drug should be recorded as medical history on the applicable eCRF page. All AEs occurring from the first dose of study drug until 28 days after the last dose of study drug must be recorded on the AE eCRF.

All SAEs (related and unrelated) must be reported to the Sponsor within 24 hours of the Investigator's knowledge. This should be done by faxing/emailing the completed SAE Report Form to the number provided on the SAE Report Form. After the EOS Visit, only new treatment-related SAEs need to be captured on the AE eCRF and reported to the Sponsor.

Investigators must follow subjects with AEs/SAEs until the event has resolved, the condition has stabilized, withdrawal of consent, the subject is lost to follow up or death OR until the EOS Visit, whichever occurs first. New and ongoing treatment-related SAEs should be followed beyond the EOS Visit. If the subject dies, this should be captured as the outcome of the AE unless no link between the AE and the subject death can be established, in which case the AE will be marked as ongoing and the death will be reported as a separate event.

If a subject is lost to follow up, this should be captured accordingly within the AE eCRF and on the follow up SAE report.

The Sponsor or designee is responsible for notifying the relevant regulatory authorities of applicable suspected unexpected serious adverse reactions (SUSARs) as individual notifications or through periodic line listings. It is the Principal Investigator's responsibility to notify the Institutional Review Board (IRB) or IEC of all SAEs that occur at his or her site. Investigators will also be notified of all unexpected, serious, drug-related events (7/15 Day Safety Reports) that occur during the clinical trial. Each site is responsible for notifying its IRB or IEC of these additional SAEs.

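### After an early-termination visit no further safety contact is scheduled, and the protocol's rules conflict on whether new adverse events must still be captured

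*Protocol*

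**What the plan says.** **Leaving early (protocol 6.9).** "If a subject withdraws from the study prematurely, assessments scheduled for the EOS Visit should be performed as soon as possible". The next sentence adds the later contact: "If a subject refuses further assessment, the subject should be contacted for safety evaluations". It falls about 28 days after withdrawal and covers AEs, concomitant medication and possible pregnancy. No other early leaver is given it. For withdrawals caused by an AE, "If the reason for withdrawal is an AE, monitoring should continue until the outcome is evident". The section also recognises a subject who "withdrew his/her consent for study drug treatment but will continue further participation in the study".

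**Duty to record.** Section 10.7 requires AEs from first dose "until 28 days after the last dose of study drug must be recorded on the AE eCRF". Section 10.1.2 requires SAEs "within 28 days following the cessation of treatment, whether or not judged to be related to the study, must be recorded". Section 6.10 says safety data will be collected from everyone given at least one dose. None of these exempts early leavers.

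**Limits on that duty.** Section 10.7 also has open events followed to the first of several end points, finishing with "the subject is lost to follow up or death OR until the EOS Visit, whichever occurs first". Treatment-related SAEs are the exception. After the EOS Visit, only new treatment-related SAEs need to be captured.

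**Which visit is the EOS Visit.** Tables 5 and 6 put early termination and end of study in one column. The visit lists in the SAP mock tables and listings likewise combine Day 28 with early termination.

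**Analysis.** The safety endpoint is primary through Day 7 and secondary through Day 28 (5.2.1, 5.2.2). The SAP keeps every dosed subject in the safety population (4.1.2), imputes no missing safety data (14), and censors survival at study exit, taking the date of death from a fatal SAE record (11.1.2).

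**The concern.** The scheduled contact depends on how cooperative the subject is, and in the wrong direction. Someone who refuses assessment is telephoned about four weeks later. Someone who comes in for the early visit has completed what the schedule calls the EOS visit, after which section 10.7 narrows capture to treatment-related SAEs and no one is told to call.

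The endpoint counts events whatever their judged cause, and includes ICU transfer, intubation, vasopressor use and death. These are the events that could follow an early exit in a patient with pneumonia and be judged unrelated to study drug. An unrecorded event shows in the AE tables as no event, because the subject stays in the denominator and nothing is imputed. A death after early exit that has no SAE record is outside the survival analysis.

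Leaving because of an AE or clinical deterioration is plausibly related to later risk, so the missing follow-up would not be random. Section 6.10 replaces only non-informative losses, so these subjects are not replaced. Escalation after each cohort rests on Day 7 safety for all its subjects (6.1, 6.4).

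**Working it through.** **1. The rules side by side, for a subject seen at an early visit and then gone**

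| Event after the early visit | 28-day recording rule (10.1.2, 10.7) | Post-EOS rule (10.7), if the early visit counts as EOS | Scheduled contact to find it (6.9) |
|---|---|---|---|
| New SAE judged treatment-related | record | record | none |
| New SAE or death not judged related | record | not required | none |
| New non-serious AE | record | not required | none |
| Course of the AE that caused withdrawal | record; 6.9 monitors to outcome | follow-up ends unless it is a treatment-related SAE | none specified |

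Rows two and three are a direct conflict. Row four is a conflict between 6.9 and 10.7. The last column is empty whichever rule a site follows.

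**2. Dates, by example.** Assume a multiple-dose subject is withdrawn on Day 2 and has the early visit on Day 3. The documents give no withdrawal timing.

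- Primary window: Days 4 to 7 have no scheduled contact, 4/7 = 57%.
- Secondary window: Days 4 to 28 have none, 25/28 = 89%.
- Recording window: with the last dose on Day 1 or 2, it ends on Day 1 + 28 = 29 or Day 2 + 28 = 30. The recording duty therefore covers all the days just counted; only the means of finding events is missing.
- A refuser withdrawn on the same day is contacted at about Day 2 + 28 = 30, after both endpoint windows close.

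If the early visit were on Day 2, the uncovered spans would be 7 − 2 = 5 days and 28 − 2 = 26 days.

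**3. What one subject is worth.** The plan's own figure is the per-dose row of protocol Table 7: with n = 6 and a true rate of 32%, a 90% chance of seeing at least one AE of a given type.

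- Formula: P(at least one) = 1 − (1 − p)^n. For n = 6: 1 − 0.68^6 = 90.1%. The row reproduces.
- The 90% upper bound when no event is seen is 1 − 0.10^(1/n). For n = 6 it is 31.9%.

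Now suppose k of the 6 subjects are unobserved for a late event:

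| Unobserved | Effective n | P(at least one) at 32% | 90% upper bound at zero events |
|---|---|---|---|
| 0 | 6 | 90.1% | 31.9% |
| 1 | 5 | 85.5% | 36.9% |
| 2 | 4 | 78.6% | 43.8% |

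One missed event changes an observed rate in an arm of six by 1/6 = 17 percentage points. The table applies only to event types that would arise after the early visit. Events before it are unaffected.

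**The case against.** The case that this is adequately covered has real substance.

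- **The recording duty is explicit.** Sections 10.1.2, 10.7 and 6.10 cover every dosed subject to 28 days after treatment. This stands. A reader might infer that cooperative early leavers are not followed at all, and the documents do not support that. What is missing is a scheduled means of meeting the duty, and section 10.7's own post-EOS sentence contradicts it.
- **AE-driven withdrawals are monitored.** Section 6.9 says so, and this too stands. It covers the AE that caused withdrawal, not new events.
- **Subjects do not drop out of the endpoints.** A reader might infer that they do, or that they are counted as wholly event-free. In fact they remain in the safety population, protocol 11.3 carries AEs forward, the triggering AE is tabulated, and censoring survival is not the same as recording survival. Only new events after the visit are exposed.
- **Stopping drug need not mean leaving.** Section 6.9 lists reasons for which participation may, not must, be discontinued, and allows for staying on study off drug. The point is therefore confined to subjects who actually leave the study.
- **The EOS Visit may already mean Day 28.** Section 6.1 places it there, and 6.9 can be read as borrowing its assessments ("assessments scheduled for the EOS Visit should be performed as soon as possible") without redefining the visit. Refusal of further assessment could also include someone who attends once and then declines more. Both readings are available, but the merged column in Tables 5 and 6 and the combined visit label in the SAP point the other way. A site could reasonably follow either.
- **The percentages come from a chosen example.** Agreed: 57% and 89% follow from picking Day 3 and are not estimates of loss.

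**Conclusion.** The protocol conflicts with itself on safety capture after early withdrawal. One set of rules requires all AEs and SAEs for 28 days after treatment. Another, applied to an early-termination visit that the schedules merge with EOS, requires only new treatment-related SAEs. The one contact that would resolve this in practice is written only for refusers. New non-serious AEs, and SAEs, ICU transfer, intubation, vasopressor use or death not judged treatment-related, can therefore go unrecorded in subjects who still count in the denominator.

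The conclusion rests on a site treating the early visit as the EOS Visit, which the documents permit but do not state. Its size is unknown because no withdrawal rate is given, and with no early leavers it is nil. Within an arm of six, one subject unobserved for late events lowers the Table 7 detection probability from 90.1% to 85.5%. That loss could rise with dose if early exit does, which is an assumption. This should be corrected in the text; it does not invalidate the design.

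**What to change.** 1. **Section 6.9:** apply the existing AE contact, with vital status added, to every dosed subject who leaves early, whether or not the early visit took place, unless the subject declines contact. Time it so that status through Day 7 and through Day 28 is obtained. A call 28 days after withdrawal meets this for the final analysis, since withdrawal on Day 1 already gives Day 29.
2. **Section 10.7:** state that an early-termination visit is not the EOS Visit that ends AE and SAE capture, so that the 28-day recording window applies to all dosed subjects. Make the column heading in Tables 5 and 6 consistent with this.
3. **Sections 6.9 and 10.7:** reconcile monitoring of the withdrawal AE to its outcome with the cut-off at the EOS Visit.

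The cost is wording plus one call per early leaver, of a kind the protocol already provides for refusers. If Day 7 status is also wanted in time for the cohort review, a second short call is needed. Keeping early leavers on the Day 7, 14 and 28 visits would go further, but that is not free of extra procedures, because those visits include laboratory and biomarker sampling.
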